## ABSTRACT

In the United States, depot medroxyprogesterone acetate (DMPA) is frequently administered prior to hospital discharge with the belief that women who delay initiation of DMPA may face higher risk of unintended pregnancy and that administration postpartum has little to no negative effect on breastfeeding. Administering DMPA to breastfeeding women has not been widely questioned because the limited existing studies do not show any adverse impact of DMPA on breastfeeding. However, these studies used inappropriate control groups and did not control for prior lactation experience.(1-3) We recently conducted a randomized controlled trial (RCT) which found that significantly fewer women who underwent immediate postplacental levonorgestrel-releasing IUD (LNG-IUD) placement continued to breastfeed at 6 months compared to those who underwent insertion at 6-8 weeks postpartum.(4) Since systemic levels of progestins are much less with the LNG-IUD compared to DMPA, we became concerned about potential effects of administering DMPA immediately postpartum.

We therefore propose to enroll 184 women who plan to breastfeed and use DMPA postpartum in a RCT to investigate whether the timing of postpartum administration of DMPA (prior to hospital discharge vs. 4-6 weeks postpartum) affects the duration or exclusivity of breastfeeding among women who plan to breastfeed their infants. Secondary outcomes will include rates of use of highly effective contraception (defined as DMPA, IUD, implant, sterilization, or lactational amenorrhea) and postpartum depression. Outcomes will be assessed by phone at 2, 4, 6, 8, 12, 16, 20, 24, and 28 weeks postpartum.

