### HYPOTHESES:

1. Women who receive DMPA 4-6 weeks after delivery will be more likely than women who receive DMPA prior to hospital discharge to exclusively breastfeed for 6 months.
2. Women who receive DMPA 4-6 weeks after delivery will be as likely as women who receive DMPA prior to hospital discharge to use highly effective contraception (i.e. DMPA, intrauterine device (IUD), implant, sterilization, or lactational amenorrhea) at 6 months after delivery.
3. Women who receive DMPA 4-6 weeks after delivery will be no more likely than women who receive DMPA prior to hospital discharge to develop postpartum depression as measured by the Edinburgh Postnatal Depression Scale.(5)

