#### *OUTCOME ASSESSMENTS*

- A questionnaire about breastfeeding (including psychosocial factors related to breastfeeding and introduction of alternatives to breastmilk) and contraceptive use will be administered at each contact. Timing of lactogenesis II will be assessed at Week 2 unless it occurred prior to discharge. Timing of postpartum sexual activity initiation will also be assessed. At any point when the subject reports cessation of breastfeeding, a questionnaire will be administered to assess reasons for discontinuation.

- The Edinburgh Postnatal Depression Scale (EPDS) will be administered at each contact as a screening tool for postpartum depression.(5) If a subject scores  $\geq 12$  on the EDPS, she will be referred to the Magee Behavioral Health clinic or to a behavioral health clinic of her choice and her primary obstetrician or midwife will be notified.
- Subjects will be asked if they had any visits with their primary obstetrician, midwife, or any other provider since the last contact. Records will be requested from all reported visits.
- The next telephone contact will be scheduled (when applicable).

**5.8 Data analysis:** Analysis will be performed using Stata 10 (StataCorp LP, College Station, TX).

- 1) The primary analyses will use intention-to-treat data. The intention-to-treat group will be defined as all randomized subjects. Infants who are fed pumped breastmilk will be considered as breastfeeding. Exclusive breastfeeding will be defined as breastfeeding without introduction of alternatives to breastmilk. A secondary analysis looking only at women who received at least one injection of DMPA will also be performed.
- 2) Survival analysis will be used for all time series data, including time to discontinuation of breastfeeding and time to introduction of alternatives to breastmilk. Data will be censored at the last date of contact. Breastfeeding will be the outcome variable. The log-rank test will be used for unadjusted comparison of the groups and presented graphically using a Kaplan-Meier curve. Cox proportional hazards model will be used to control for age, race, education, marital status, and prior breastfeeding experience while examining the association between timing of DMPA administration and discontinuation of breastfeeding.

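### Section 5.8 states a covariate-adjusted Cox model for stopping breastfeeding but not for loss of exclusivity, the endpoint of Hypothesis 1; a possible gain in precision is forgone.

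*Combined protocol and SAP*

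**What the plan says.** Hypothesis 1 in section 1 expects women given DMPA at 4-6 weeks to be "more likely than women who receive DMPA prior to hospital discharge to exclusively breastfeed for 6 months". Section 5.8 item 1 fixes the meaning of that endpoint: "Exclusive breastfeeding will be defined as breastfeeding without introduction of alternatives to breastmilk". Its time-to-event form is therefore time to introduction of alternatives.

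Item 2 of section 5.8 puts two outcomes under survival analysis: "time to discontinuation of breastfeeding and time to introduction of alternatives to breastmilk". It then gives the unadjusted method, "The log-rank test will be used for unadjusted comparison of the groups", with a Kaplan-Meier curve. A Cox model follows, adjusting for prior breastfeeding experience, marital status, education, race and age, and its stated purpose is "examining the association between timing of DMPA administration and discontinuation of breastfeeding". Item 3 adds chi-square or Fisher's exact tests for proportions. No other part of the document describes an adjusted analysis of exclusivity.

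**The concern.** The same paragraph separates the two outcomes and then names only one of them for the adjusted model. The one left out is the one Hypothesis 1 is about.

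Two things are at stake. First, in a proportional hazards setting, adjusting for baseline factors that predict the outcome usually raises power for the treatment comparison, because the hazard ratio that ignores them is pulled towards 1. The covariates are already listed for the discontinuation model, so leaving them out for exclusivity saves nothing. Second, if both models were intended, the text does not say so, nor which result would decide the hypothesis. That leaves a choice that could be made after the data are seen.

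The protocol itself treats one of these covariates as important: the Abstract faults earlier studies because they "did not control for prior lactation experience".

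**Working it through.** **1. The plan's own sample size.** Section 5.9 uses 0.35 vs 0.60 still breastfeeding at 6 months, two-sided alpha 0.05, Fisher's exact test and 80% power. Exact enumeration gives power 0.7992 at 69 per group and 0.8095 at 70, so 70 per group is reproduced. Inflation: 140 / (0.90 × 0.85) = 183.0, against 184 stated. The sizing uses no covariates.

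**2. Does the unadjusted log-rank test fall short of the plan?** At the design rates, assuming proportional hazards:
- Hazard ratio = ln 0.35 / ln 0.60 = 2.06
- Events = 70 × (0.65 + 0.40) = 73.5
- Schoenfeld: √73.5 / 2 × ln 2.06 − 1.96 ≈ 1.13, so power ≈ 0.87

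This exceeds the 0.81 of Fisher's test. These rates are for breastfeeding continuation. Section 5.9 gives none for exclusivity.

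**3. What would adjustment add for exclusivity?** From the protocol: 184 × 0.90 ≈ 165 randomized (also stated in the Budget Justification), or about 82 per arm, and 15% loss to follow-up. Assumed: exponential times, conditional hazard ratio 1.6, about 80% having introduced alternatives by week 28 before dropout, uniform dropout times, 50% with prior breastfeeding experience, and the covariate strengths below. Two-sided 5% tests; simulation error is about 1 point.

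| Covariate strength (assumed) | Unadjusted | Adjusted Cox |
|---|---|---|
| Not prognostic | 74% | 74% |
| Prior-experience HR 1.5, other covariates SD 0.2 | 70% | 73% |
| HR 2.0, SD 0.35 | 62% | 72% |
| HR 2.5, SD 0.5 | 56% | 72% |

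The SD is that of the other covariates' combined effect on the log hazard. The gain runs from nil to 72 − 56 = 16 points. The average unadjusted hazard ratio falls from about 1.60 to about 1.46 across the rows, which is the attenuation at work.

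**4. A second set-up.** The fall in the unadjusted column partly reflects holding the conditional hazard ratio at 1.6. Holding instead the 6-month exclusive rates at an assumed 0.10 vs 0.25, with 70 per group, no dropout and a combined covariate SD as shown, power is:
- SD 0: 79% unadjusted, 78% adjusted
- SD 0.3: 81%, 84%
- SD 0.5: 82%, 89%
- SD 1.0: 85%, 99%

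Here unadjusted power does not fall as the covariates strengthen, and the gain runs from nil to about 14 points.

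**5. Chance imbalance in prior experience.** Section 5.5 describes no stratification. At an assumed 50% prevalence, the SD of the difference between arms is √(2 × 0.25 / 82) = 0.078, so the chance of a gap above 10 points is about 20%. With a prior-experience hazard ratio of 2.0, a 10-point gap shifts the log hazard ratio by 0.10 × ln 2 = 0.07. The standard error with about 125 events is 2 / √125 = 0.18. The shift is well under half a standard error, and the test's error rate already allows for it.

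**The case against.** The best case for the plan has four parts.

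- **Loose drafting.** Item 2 opens with both outcomes and then calls breastfeeding the outcome without qualification, so the Cox sentence may be shorthand for both. The text does not exclude that reading. It stands as a reason to treat this as a clarification rather than an error, but it does not remove the need for the clause.
- **Nothing is invalid or lost.** A reader might infer that the trial loses power against its plan, or that the unadjusted comparison is biased. The documents support neither. Randomization makes the log-rank test valid, and section 5.9 sized the trial on an unadjusted test. This stands in full.
- **The log-rank test is not the only test.** A reader might infer that it is. Item 3 also allows chi-square or Fisher's exact tests, which suit a 6-month proportion. That is correct, though those tests are unadjusted too.
- **The Abstract's complaint is about other studies.** Section 2 says none of the studies reviewed for the US contraceptive eligibility criteria was randomized and that they may be subject to residual confounding. Randomization answers that. The complaint shows that the authors see prior lactation experience as prognostic; it does not show that an unadjusted randomized comparison is confounded. The imbalance arithmetic agrees.

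It is also fair to say that an adjusted result merely placed beside the log-rank test would not raise the power of whichever test decides, and could add a second unranked test of the same hypothesis. The fix has to deal with that.

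**Conclusion.** The gap holds as a matter of text: no adjusted analysis is stated for the endpoint of Hypothesis 1, although one is stated for the companion endpoint with covariates that serve both. The consequence is an opportunity forgone, not a shortfall. In the main set-up the gain in power is nil with non-prognostic covariates, about 3 points with modest ones, 10 with moderate ones and 16 with strong ones. Those sizes rest on an assumed hazard ratio, event rate, prevalence and covariate strength; the protocol supplies only the 15% dropout and the approximate arm size. Nothing in the documents says which row applies.

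It would go too far to infer that adjustment would secure the power for Hypothesis 1. Section 5.9 gives no exclusive-breastfeeding rates, so that power is not established under either analysis.

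**What to change.** In section 5.8 item 2:

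- Extend the Cox sentence so that it covers time to introduction of alternatives to breastmilk as well as discontinuation, with the covariates already listed.
- Report the adjusted hazard ratio and its 95% CI for each outcome.
- State, before the data are examined, whether the adjusted Cox result or the log-rank result decides Hypothesis 1, and label the other as supportive. The power gain is realised only if the adjusted result decides.

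The cost is a clause and a sentence in the plan and one more model run. The covariates are already needed for the discontinuation model, so no new data are required.

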### **5.9 Number of subjects and statistical power**

We previously found in a randomized study comparing postplacental and delayed LNG-IUD insertions that only 9% of subjects receiving a postplacental LNG-IUD were breastfeeding at 6 months compared to 41% of subjects receiving a delayed LNG-IUD.(4) We expect breastfeeding continuation rates will be higher in this study since we will be recruiting women who intend to breastfeed. A sample size of 70 per group achieves 80% power ( $\beta=0.20$ ) to detect a difference of 25% between the null hypothesis that the proportion of breastfeeding continuation at 6 months is 0.60 for both groups and the alternative hypothesis that the proportion in group 1 is 0.35 with a significance level of 0.05. With an estimated 10% discontinuation rate prior to randomization and 15% loss-to-follow-up, we plan to enroll 184 subjects

total. Sample size calculations were performed with the two-sided Fisher's Exact test using PASS 2005 (NCSS, Kaysville, UT).

Group 1 (on discharge)	Group 2 (4-6 weeks)	Sample size per group	Total sample size	Including 10% discontinuation/15% LTFU
0.15	0.4	56	112	147
0.25	0.5	64	128	168
0.35	0.6	70	140	184
0.45	0.7	69	138	182

**5.10 Project management:** The study will be coordinated by the Center for Family Planning Research, located in Magee-Womens Hospital at the University of Pittsburgh, which has performed a broad array of family planning research since 1994. The principal investigator and the research coordinator will be responsible for daily monitoring of subject safety. Enrollment, outcomes, and adverse events will be reviewed during biweekly meetings of the investigators and staff. The office has locked storage areas for maintaining subject files. All computers used for database management have firewalls and antivirus software that are updated regularly.

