## 1. SPECIFIC AIMS AND HYPOTHESES

### SPECIFIC AIMS:

To compare the effect of administering postpartum intramuscular (IM) depot medroxyprogesterone acetate (DMPA) prior to hospital discharge compared to 4-6 weeks after delivery on: 1) exclusivity and duration of breastfeeding; 2) use of highly effective contraception; and 3) postpartum depression

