## 2. PREVIOUS RESEARCH

Postpartum contraception is important because unintended pregnancy rates range from 10%-20% in the first year postpartum.(6, 7) Lactational amenorrhea (LAM) can be effective contraception for up to 6 months.(8) However, many US women stop breastfeeding soon after delivery. By two weeks postpartum, an estimated 59% of US women started supplementation (2) and 37% of women stopped breastfeeding.(9) If sexually active and not using contraception, such women are at risk for unintended pregnancy.

Postpartum visits in the US generally occur 4-6 weeks after delivery.(10) Although 85% of women return for postpartum visits,(11) approximately half of women initiate sexual activity before six weeks postpartum and 82% are sexually active by 12 weeks postpartum.(12) Since ovulation can occur by 4 weeks postpartum in non-breastfeeding women,(13) experts recommend that women who are not exclusively breastfeeding should initiate contraception by 3 weeks postpartum.(14) Some also recommend that the postpartum visit should occur by 2-4 weeks postpartum in order to address contraception, breastfeeding, and postpartum depression,(14, 15) since postpartum depression affects 10%-15% of mothers (16) and can be associated with poor maternal-infant interactions and attachment.(17) Studies of the association of depression and breastfeeding discontinuation are conflicting.(18-20) One study of norethisterone enanthate given within 48 hours of delivery found an increased risk of postpartum depression,(21) but no studies have examined the effect of timing of DMPA administration on postpartum depression, contraceptive use, or breastfeeding.

Breastfeeding has many benefits, including immunologic protection and nutrition for the infant, more rapid uterine involution, decreased postpartum bleeding, and improved infant-bonding.(22) Exclusive breastfeeding for at least six months is recommended by the American College of Obstetricians and Gynecologists and the World Health Organization.(22, 23) However, only 41% of children in the National Immunization Survey were breastfed for 6 months.(24)

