#### **5. RESEARCH DESIGN AND METHODS**

**5.1 Overview:** We will enroll 184 pregnant subjects who plan to breastfeed and use DMPA for postpartum contraception. Subjects will be randomized to IM DMPA administration prior to hospital discharge or at 4-6 weeks after delivery (in the office of their primary obstetrician or midwife). Follow-up phone calls will be conducted at 2, 4, 6, 8, 12, 16, 20, 24, and 28 weeks after delivery. We will assess duration of exclusive and total breastfeeding, contraceptive use at 3 and 6 months, and rates of postpartum depression.

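### The 80% power in section 5.9 is for breastfeeding continuation at 6 months, but Hypothesis 1 is about exclusive breastfeeding, and no primary breastfeeding endpoint or test is named

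*Combined protocol and SAP*

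**What the plan says.** Hypothesis 1 (section 1) states that women given DMPA at 4-6 weeks "will be more likely than women who receive DMPA prior to hospital discharge to exclusively breastfeed for 6 months". Hypotheses 2 and 3 concern contraception and depression, so this is the only breastfeeding hypothesis.

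Section 5.9 takes as its null that "the proportion of breastfeeding continuation at 6 months is 0.60 for both groups", with 0.35 in Group 1 under the alternative. It gives 70 per group, 80% power, significance level 0.05 and a two-sided Fisher's exact test, and 184 enrolled after allowances for attrition. Its precedent is an earlier IUD trial with 9% versus 41% breastfeeding at 6 months, not exclusively breastfeeding.

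The plan treats the two as different outcomes. Section 5.1 says "We will assess duration of exclusive and total breastfeeding". Section 5.8 gives exclusive breastfeeding its own, stricter definition, and item 2 lists "time to discontinuation of breastfeeding and time to introduction of alternatives to breastmilk".

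On ranking, the Abstract says "Secondary outcomes will include rates of use of highly effective contraception" and adds postpartum depression, which leaves breastfeeding as the primary domain by implication. Within it, Aim 1 covers "exclusivity and duration of breastfeeding" without ranking the two. The word primary in section 5.8 item 1 describes the intention-to-treat analysis, not an endpoint.

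On the test, section 5.8 item 2 says "Breastfeeding will be the outcome variable. The log-rank test will be used for unadjusted comparison of the groups", with a Cox model for discontinuation. Item 3 provides chi-square or Fisher's exact tests for proportions.

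**The concern.** The plan's only power statement and only significance level belong to an endpoint other than the one in its breastfeeding hypothesis. Two problems follow.

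- A null result on exclusive breastfeeding could be read as coming from a trial with 80% power to detect an effect on it. The plan does not show that.
- Exclusivity and continuation can disagree. If one comparison is significant and the other is not, nothing prespecified says which one answers the trial's question, so the choice could be made after the results are seen.

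The planning rate of 0.60 cannot simply be carried over to exclusive breastfeeding. Section 2 gives one related background figure: "By two weeks postpartum, an estimated 59% of US women started supplementation". That leaves at most 41% still exclusive at that point, while the same section puts 37% as having stopped altogether, so 63% were continuing. These are US figures from two different sources. Women in this trial intend to breastfeed, and their rates may be higher.

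**Working it through.** **1. Reproduce the plan's figure.** Inputs from section 5.9: 0.35 versus 0.60, two-sided Fisher's exact test, alpha 0.05. Power is the sum, over all pairs of binomial counts, of the probability of each pair whose Fisher p-value is at most 0.05.

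- 70 per arm gives 0.809, and 69 per arm gives 0.799, so 70 is right.
- Enrolment: 140 / (0.90 × 0.85) = 183.007, rounded up to 184, as stated.

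The sample size is therefore correct for breastfeeding continuation at 6 months.

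**2. The same endpoint under the log-rank test of section 5.8.** This was simulated with constant hazards and follow-up to 6 months (rejection rate under the null 0.050).

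- 70 per arm, no loss: power about 0.87.
- The Budget Justification expects 165 at the randomization visit, and 165 / 2 = 82.5. With 82 per arm and 15% lost at random and censored, power is about 0.89.

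**3. Exclusive breastfeeding.** The plan gives no rates, so some must be assumed. Take a Group 2 rate of 1 − 0.59 = 0.41 as an illustration only: it is a two-week US background figure, not a limit for this trial. The Group 1 rate then depends on which feature of the planned effect is kept:

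- Difference: 0.60 − 0.35 = 0.25, so 0.41 − 0.25 = 0.16.
- Risk ratio: 0.35 / 0.60 = 0.583, so 0.41 × 0.583 = 0.239.
- Odds ratio: (0.35/0.65) / (0.60/0.40) = 0.359. Then (0.41/0.59) × 0.359 = 0.249, and 0.249 / 1.249 = 0.200.
- Hazard ratio: ln 0.35 / ln 0.60 = 2.055, so 0.41 to the power 2.055 = 0.160.

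| Kept from the plan | Group 1 vs Group 2 | Fisher power, 70 per arm | Log-rank power, 70 per arm, no loss |
|---|---|---|---|
| 25-point difference | 0.16 vs 0.41 | 89% | 95% |
| Risk ratio 0.583 | 0.239 vs 0.41 | 52% | 63% |
| Odds ratio 0.359 | 0.200 vs 0.41 | 73% | 83% |
| Hazard ratio 2.055 | 0.160 vs 0.41 | 89% | 95% |

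Other assumed Group 2 rates, by Fisher's exact test:

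- At 0.50: 83% (difference), 65% (risk ratio), 78% (odds ratio), 86% (hazard ratio).
- At 0.20: 21% (risk ratio), 44% (odds ratio), 83% (hazard ratio). A 25-point drop is impossible once the Group 2 rate is below 0.25.

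**4. Fisher's exact test in all randomized women.** The 0.81 in step 1 is for 70 women per arm with a known outcome. Fisher's test cannot use censored women, so those lost must be classified or left out. If the 15% lost are counted as not breastfeeding (an assumption), the rates become 0.35 × 0.85 = 0.2975 and 0.60 × 0.85 = 0.51. Power with 82 per arm is then 74.5%.

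**The case against.** The strongest reply is that the intended lead endpoint can be inferred. The closing paragraph of section 2 and the Rationale in section 3 both frame the breastfeeding question as continuation, the Cox model in section 5.8 is for discontinuation, and section 5.9 sizes continuation. This stands as far as it goes. It makes Hypothesis 1 the outlier, but does not remove the conflict with it, and still no section says which endpoint is primary.

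A second reply is that the section 5.9 table already covers lower rates: 0.25 versus 0.50 needs 64 per group and 0.15 versus 0.40 needs 56, both below 70. This also stands in part. If a 25-point difference held for exclusive breastfeeding at such rates, 70 per arm would be enough. But those rows are continuation scenarios, and the plan gives no reason to expect that difference in exclusivity.

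A third reply is that the two tests are not in real conflict, since section 5.8 item 3 already allows Fisher's exact test for a 6-month proportion. That is right. What remains is that neither test is labelled primary.

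In the other direction, a reader might infer that the trial is underpowered for exclusive breastfeeding, or that 184 is a wrong number. The documents support neither. The power depends on rates they do not give, several of the scenarios above exceed 80%, and the sample size reproduces.

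**Conclusion.** The point holds as a mismatch between the stated hypothesis and the sized endpoint, with no primary breastfeeding endpoint or test named. The 80% is correct for continuation at 6 months: 0.81 by Fisher's exact test with 70 evaluable per arm, and about 0.87 by log-rank under constant hazards. For exclusive breastfeeding the power is unknown, and it is not shown to be low. The spread at an assumed rate of 0.41 shows how far the answer turns on assumptions the plan does not state. This should be fixed, because the plan as written lets either outcome answer its main question. The finding itself rests on the text alone; only the illustrative powers depend on assumed rates and effect scales.

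**What to change.** By a dated amendment, made before any comparison by group:

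- Reword Hypothesis 1 to breastfeeding continuation through 6 months in all randomized women, and use the same endpoint in sections 1, 5.8 and 5.9.
- Make exclusive breastfeeding a secondary outcome with no power claim.
- Name the log-rank test already in section 5.8 as the primary test and keep the censoring described there. On the assumptions in the working, it holds more than 80% power at the sized rates, including with 15% random loss.
- If Fisher's exact test is made primary instead, state how women lost before 6 months are counted, since that choice can take power below 80%.
- If exclusive breastfeeding is to stay primary, state its expected rates in section 5.9 and replace the 80% with the power that 70 per arm gives at those rates under the named test.

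The cost is wording in three sections. No extra women, contacts or data are needed, because both outcomes are already collected. The trial is already enrolling (section 5.11 reports 62 participants since the modification of 8/16/13), which is why the date and the timing before any comparison by group matter. The downside is that exclusive breastfeeding becomes secondary or, if it stays primary, the stated power may look less favourable.
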